5.7 Aims for UH3 Phase

Aim 1: To determine whether inserting a description of age-specific prevalence of imaging findings among asymptomatic subjects into lumbar spine imaging reports decreases back-related interventions during the subsequent year.

Aim 1a: To determine if inserting epidemiological evidence reduces RVUs attributable to spine interventions.

Hypothesis 1a: After primary care clinics are randomly assigned to receive the modified report, they will have a lower average overall RVU (technical and professional) per imaged-patient attributable to spine interventions than clinics that are not receiving the modified reports.

We will calculate an overall spine-related RVU for each patient in the study by summing all RVUs attributable to spine-interventions within one and two years after the date of return of the index image report (the plain film, MR or CT of the lumbar spine imaging study whose report either does or does not contain the epidemiological benchmark data). For each patient accrual period in Figure 3, we will calculate a total spine-related RVU per primary care provider who orders at least one lumbar imaging exam in Table 2. We will aggregate spine-related RVUs across the study-eligible patient panel. The calculated primary care provider RVU will serve as the primary outcome measure of this study. As noted, we will also apply standardized CMS-based costs to RVU calculations.

We will use generalized linear mixed models with jackknifed standard to model the change in post-intervention RVU from pre-intervention RVU. We will use random effects for the clinic and for the effect of intervention defined by the indicator of exposure to the LIRE intervention. We will use a three-month pre-intervention washout period where patients with index visits in this window will be excluded from the analysis. We will adjust the model for period of time (period 0 through period 5) as a fixed effect to adjust for general calendar trends in RVUs. We will also adjust the model for the type of image ordered at the initial index visit as a categorical variable (plain film, CT, MR).

Aim 1b: To determine if inserting epidemiological evidence decreases subsequent opioid prescriptions.

Hypothesis 1b: Clinics that are randomly assigned to receive the modified imaging reports will have a lower rate of subsequent opioid prescriptions than clinics whose patients do not receive modified reports.

Our pilot work suggested that including epidemiological evidence was associated with a nearly 3.5-fold reduction in opioid prescriptions. We feel that it is important to test this hypothesis given the growing recognition that the overuse of opioids is an important issue in the management of back pain patients.

We will calculate a binomial outcome of the number of patients (out of the eligible patient panel) with a prescription for opioids that occurred after the lumbar spine imaging report was finalized. We will examine this for each primary care provider across each of the six patient accrual periods. We will utilize a generalized linear mixed model to assess the impact of the LIRE intervention on subsequent written opioid prescription rates. Since some patients will already have an active prescription for opioids at the time of the index visit, we will also conduct a subgroup analysis by conducting analyses separately for those patients with and without an active prescription at baseline. As described earlier, we will convert all prescriptions into MEDs. This will allow us to examine temporal trends in not only prescriptions but also dose.

Aim 1c: To determine if inserting epidemiological evidence decreases subsequent cross-sectional imaging (magnetic resonance (MR) and computed tomography).

Hypothesis 1c: Clinics that are randomly assigned to receive the modified imaging reports will have a lower rate of subsequent cross-sectional imaging than clinics whose patients do not receive modified reports.

The number of patients who receive cross-sectional re-imaging within 1 and 2 years (out of the eligible patient panel) will be calculated as a binomial outcome measure for each primary care provider across each of the six patient accrual periods. We will again utilize a generalized linear mixed model to assess the impact of the LIRE intervention on subsequent rates of cross-sectional reimaging, including random effects for the baseline rate of cross-sectional re-imaging and for an indicator of exposure to the LIRE intervention. We will adjust the model for period of time (period 0 through period 5) as a fixed effect to adjust for general longitudinal trends in re-imaging rates. We will also adjust the model for the type of image ordered at the initial index visit as a categorical variable (plain film, CT, MR).

Aim 1d: To explore whether adding epidemiological evidence decreases overall costs of care for low back pain based on CMS reimbursement.

Hypothesis 1d: Clinics that are randomly assigned to receive the modified imaging reports will have lower back pain-related estimated payer costs than clinics whose patients do not receive modified reports.

We will apply CMS-based reimbursement amounts to RVU calculations in order to standardize unit cost estimation among our sites. We will use CPT and diagnostic codes to determine whether interventions are associated with back pain, and multiply the total back-treatment related RVUs at sites by the unit price payment amounts for respective RVU calculations.

Table 5: Sample of RVUs and CMS-based payment amounts for lumbar imaging (US\$ 2012)

CPT	Diagnostic Imaging Exam	Hospital (facility)		Professional		
		Hosp RVU	Hosp payment	Pro wRVU	Pro tRVU	Pro payment
72100	2 view x-ray exam lower	0.6399	\$48.22	0.22	0.34	\$12.08

	spine					
	4 view x-ray exam lower					
72120	spine	0.6399	\$48.22	0.22	0.35	\$12.47
72131	CT lumbar spine w/o dye	2.746	\$206.54	1	1.44	\$51.57
72132	CT lumbar spine w/dye	4.2918	\$323.42	1.22	1.75	\$62.58
72133	CT lumbar spine w/o & w/dye	4.7716	\$359.59	1.27	1.82	\$65.10
72148	MRI lumbar spine w/o dye	4.8333	\$364.24	1.48	2.14	\$76.44
72149	MRI lumbar spine w/dye	6.2248	\$469.10	1.78	2.57	\$91.88
72158	MRI lumbar spine w/o & w/dye	7.6273	\$574.79	2.36	3.41	\$121.79

Aim 2: To determine whether inserting age-specific prevalence of imaging findings in asymptomatic subjects has a differential effect on subsequent back-related interventions if inserted into lumbar spine magnetic resonance (MR) and computed tomography (CT) imaging reports compared with plain films.

Hypothesis 2: Inserting epidemiological information into plain film reports will result in a greater decrease in subsequent back-related interventions than similar information put into MR and CT reports.

Our pilot work examined only MR. However, given that plain films are generally obtained earlier in the course of back pain and more frequently than cross-sectional imaging, the potential impact of inserting epidemiological information into plain film reports is large. In each separate analysis of Aim 1 outcomes, we will add an indicator of imaging modality (plain film versus MR versus CT) and an imaging modality by treatment interaction term in the model. Primary inference will be on the interaction term, where we expect that patients with more advanced imaging will have a significantly greater reduction in subsequent interventions than those who receive a plain film image.

Aim 3: To determine whether the presence of certain imaging findings influence subsequent interventions

Hypothesis 3: Inserting epidemiological information will result in a greater decrease in subsequent interventions for patients without findings that are clearly clinically important compared with patients who have clinically important imaging findings.

Our work and others have shown that certain imaging findings are likely clinically more important than others (e.g. nerve root compression, moderate to severe central stenosis, disc extrusions). To address this hypothesis, we will use the returned result from radiology to categorize imaging findings into clinically important versus not clinically important. We have identified central canal stenosis, nerve root compression and disc extrusion (a type of herniation) as the clinically most important imaging findings. This is in contrast to findings that are less clinically important (disc bulge, disc narrowing, Modic change, annular fissure, etc).

In each separate analysis of Aim 1 outcomes, we will add an indicator of clinical importance and a clinical importance by treatment interaction term in the model. Similar to Aim 2, primary inference will

again be on the interaction term, where we expect that patients without these more important findings will have a significantly greater reduction in subsequent interventions compared to patients with important findings.

Table 6: Milestones for UH3 (Implementation Phase)- Years 2-5

Year of Project	UH3 Milestone	Comment
Year 2	Final testing of intervention deployment	To be completed before Wave 1 of randomization scheduled for April, 2014
	Intervention implemented at 40% of clinical sites	Planned staggered implementation using stepped wedge design will require close monitoring of progress.
	Algorithm finalized for electronic medical record extraction and tested at all sites	This will continue the work started as UH2 Milestone #4. Each site will require a customized algorithm- hence the need for site-specific development and testing
	Protocol paper submitted for publication	We will prepare a manuscript describing our study protocol and procedures.
Year 3	Randomized intervention implemented at 80% of clinical sites	Planned staggered implementation using stepped wedge design will require close monitoring of progress.
	Medical record extraction complete for 12mo outcomes on randomization waves 1-2	Data extraction ongoing for duration of project for 12 and 24mo time-points.
	Comparison of abstraction methods for radiology reports (natural language processing vs. Amazon Turk)	
Year 4	Intervention implementation completed	All clinical sites randomized to intervention by this time.
	Medical record extraction complete for 12mo outcomes on randomization waves 3-4 and 24mo outcomes on randomization waves 1-2	
	Abstraction of radiology reports through 12mo for waves 1-4 using preferred method from yr 3	
Year 5	Medical record extraction including imaging reports complete for 12mo outcomes on randomization wave 5 and 24 mo outcomes on randomization waves 3-4	

constrained by study considerations. We anticipate enrolling ~100,000, patients who underwent lumbar spine imaging examinations across four different health systems.

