**Power for Secondary Outcome:** Using the updated clinic and provider listing, we repeated the UH2 power analyses for a reduction in subsequent opioid prescriptions. We again used an average baseline opioid prescription rate of 22%, suggested from the pilot manuscript to anchor the effect size of percent reduction in the baseline rate. A clinic-specific baseline opioid prescription rate was drawn from a Beta( $\alpha=6$ ,  $\beta=20$ ) distribution; we used this rate to draw a baseline opioid prescription rate random effect for each primary care provider using a clinic-specific log-normal distribution. We generated 1,000 simulated data sets using the effect size of a 7.5% reduction in the opioid reported in our UH2 application and evaluated each using a GLMM assuming random intercepts. With 110 clinics randomized, the study remains well powered (88.9% power) to detect a reduction in the rate of opioid prescriptions of 7.5% or larger (e.g. 22% down to 20.4%).

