**Lumbar Imaging with Reporting of Epidemiology (LIRE) Statistical Analysis Plan Revisions**

The following table includes amendments to our statistical analysis plan (SAP) that we included in statistical models for the manuscript but that we did not specify in our original SAP.

Amendments to Statistical Analysis Plan (SAP)	
Number of clinics	

 
• 110 to 98 clinics
 
	When we wrote the SAP we estimated that we would have 110 clinics participating in the trial. We dropped ten clinics prior to randomization for logistical reasons. We dropped two additional small clinics just after randomization and before the first data submission: one had closed and the other had been subsumed in another clinic.
Covariates	We made all decisions regarding covariates before we began the statistical analysis.
Covariates added	Rationale

 
• Site by time interactions
 
	Allow for differential time trends by site

 
• Gender
 
	Allow for outcome differences by gender (precision)

 
• Charlson Comorbidity Index category
 
	Comorbidity measures are associated with outcomes. We sought greater precision by including this general measure of health.

 
• Prior opioid status (opioid models only)
 
	Allow for differences in outcome between those without and those with prior opioid prescriptions (precision)
Covariates transformed	

 
• Time
 
	The SAP and protocol paper indicated that we would model time linearly as 6-month time period (t = 0, 1, 2, 3, 4, 5). Upon further thought, we decided that a more granular measure (i.e. day) would be more appropriate.

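### The supplementary opioid analysis by baseline prescription has no planned comparison of the two intervention effects, so equal effects could be misread as an effect in one group only.

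*Protocol*

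**What the plan says.** Protocol section 5.7, Aim 1b, first specifies an overall mixed-model analysis of the opioid prescription rate. It then adds a subgroup analysis, with this reason: "Since some patients will already have an active prescription for opioids at the time of the index visit". The method is: "we will also conduct a subgroup analysis by conducting analyses separately for those patients with and without an active prescription at baseline". No interaction term, contrast or rule for reading the two results together follows.

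The SAP's opioid model (Secondary Outcome Analysis) is one pooled logistic mixed model with no term for baseline opioid use. The SAP revision table adds prior opioid status to the opioid models, with the reason "Allow for differences in outcome between those without and those with prior opioid prescriptions (precision". That lets the outcome level differ between the groups, but not the intervention effect. The same table lists site-by-time terms explicitly as interactions, so the prior-opioid entry reads as a main effect.

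For Aims 2 and 3 the method differs. Protocol 5.7 places primary inference on the modality-by-treatment and clinical-importance-by-treatment interactions, and the SAP specifies Wald tests for them.

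For the opioid outcome as a whole, the SAP states that "the study remains well powered (88.9% power) to detect a reduction in the rate of opioid prescriptions of 7.5% or larger". It gives no power for either subgroup.

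**The concern.** Two separate fits answer two questions: is there an effect in patients already on opioids, and is there one in the rest? They do not answer whether the effects differ. That third question is the one a reader asks when shown the two results side by side.

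Each subgroup has less information than the whole sample, so its test has less power. When the true effect is the same in both, one result can easily reach significance while the other does not. At stake is a conclusion that the report text works only in patients with, or only in patients without, a baseline prescription, when the data do not show a difference.

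**Working it through.** **Inputs from the documents**
- Whole-sample power 88.9% for a 7.5% relative reduction from 22%: 0.22 × 0.925 = 20.35%, printed as 20.4% (SAP, Power for Secondary Outcome).
- 110 clinics and 1,824 PCPs (SAP, Design); 98 clinics after amendment (SAP revision table).
- About 100,000 patients (Protocol), so 100,000 / (1,824 × 6) = 9.1 per PCP per period.

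**Assumptions, because the documents are silent**
- Two-sided alpha of 0.05.
- The subgroups' shares of statistical information, taken from 50:50 to 10:90.
- The same log odds ratio in both groups.

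**Is 88.9% plausible?** It comes from simulation, and neither the patients per PCP nor the provider-level standard deviation is given, so it cannot be reproduced exactly. I used a generalised least squares approximation on the logit scale: five waves, six periods, clinic intercept SD 0.48 from the SAP's Beta(6, 20), and mean clinic sizes from SAP Table 1. With 9.1 patients per PCP-period it gives 94.8% without the three-month washout and 89.9% with it. Without washout, 6 patients give 83.2% and 8 give 91.9%. The stated figure is plausible and serves as the anchor.

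**Subgroup power**
- Whole-sample noncentrality: 1.960 + 1.221 = 3.181.
- Power of a subgroup with information share f: Φ(3.181 × √f − 1.960).
- Chance that exactly one is significant, for independent estimates with powers p1 and p2: p1(1 − p2) + p2(1 − p1).

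For f = 0.5: 3.181 × 0.7071 = 2.249, and Φ(0.289) = 0.614. Then 2 × 0.614 × 0.386 = 0.474.

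| Split | Power, smaller share | Power, larger share | Both | Exactly one | Neither |
|---|---|---|---|---|---|
| 50:50 | 61.4% | 61.4% | 37.7% | 47.4% | 14.9% |
| 40:60 | 52.1% | 69.3% | 36.1% | 49.2% | 14.7% |
| 30:70 | 41.4% | 75.9% | 31.4% | 54.5% | 14.2% |
| 20:80 | 29.6% | 81.2% | 24.0% | 62.8% | 13.2% |
| 10:90 | 17.0% | 85.5% | 14.5% | 73.4% | 12.0% |

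The information share is not the patient share. For example, if 20% of patients had a baseline prescription and the outcome rates were 60% and 10% (all assumed), f = 0.2 × 0.6 × 0.4 / (0.2 × 0.6 × 0.4 + 0.8 × 0.1 × 0.9) = 0.40.

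**Sensitivity of the exactly-one figure**
- *98 clinics:* noncentrality 3.181 × √(98/110) = 3.003, whole-sample power 85%; 49% at 50:50 and 62% at 20:80.
- *Effect size at 50:50:* 32% at half the design effect, 32% at 1.25 times, 15% at 1.5 times, 1% at twice.
- *Effect size at 20:80:* 56% at 1.25 times, 43% at 1.5 times, 19% at twice.
- *Shared clinic noise:* if a fraction c of the whole-sample variance is common to both groups, each subgroup's relative variance is c + (1 − c)/f, and the correlation is c divided by the square root of the product of the two variances. At 50:50, c = 0.25 gives 40% and c = 0.5 gives 31%. At 20:80 the figures are 57% and 49%.

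**Interaction test under the same conditions.** With equal effects the expected difference is zero, so a 5% test rejects 5% of the time. One million simulated pairs gave 5.0% at both 50:50 and 20:80; comparing the two separate results on the same draws gave 47% and 63%.

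**The case against.** The strongest case on the other side has four parts.

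1. *The analysis may no longer be planned.* The subgroup sentence stands only in the protocol. Protocol 5.2 refers readers to a separate analysis plan that incorporates modifications, and the SAP describes only a pooled opioid model. This stands in part: the SAP neither repeats nor withdraws the subgroup analysis, so the two documents need reconciling.

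2. *Aim 1b states no differential hypothesis.* A reader might infer that new starts versus continuing use is the main reading of Aim 1b. The documents do not support that. Hypothesis 1b concerns the overall prescription rate, and the subgroup analysis is an addition to it. Aims 2 and 3 exist to test differential effects, so the contrast with them shows what method the plan uses for such questions, not that Aim 1b poses one of equal rank.

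3. *Separate fits need not be read as two p-values.* This is true: they also give estimates and intervals, and no significance rule is stated. But the plan supplies nothing else with which to compare the groups.

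4. *The probability is conditional.* This stands in full. At 50:50 it cannot exceed 50%, so 47% is close to the worst case for that split. With no effect in either group it would be about 10% (2 × 0.05 × 0.95). The two groups share clinics and rollout dates, and the SAP model has a clinic-level random intervention effect, so some correlation is likely.

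**Conclusion.** The gap is real and limited. The protocol plans separate opioid analyses by baseline prescription, and neither document provides a test or interval for the difference in effect. Exactly one subgroup would be significant about 47% of the time at an even information split and 63% at 20:80. This rests on four conditions: an effect at the 7.5% design value in both groups, each group judged at two-sided 0.05, an assumed split, and nearly independent estimates. Larger effects or shared clinic noise lower the figure, but in most of the cases examined it stays well above the 5% of an interaction test. The exception is an effect of twice the design value at an even split (1%).

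A reader might infer that an identical effect will look one-sided half the time whatever the circumstances, or that the opioid result as a whole is in doubt. Neither follows. The first needs the conditions above, which the documents neither state nor rule out. The second fails because the overall opioid model does not depend on the subgroup fits. The point concerns how a supplementary analysis of a secondary outcome is read, and its severity is low.

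**What to change.** State in the SAP whether the Aim 1b subgroup analysis is still planned. If it is:
- Fit one opioid mixed model with a Status × prior-opioid term and time trends specific to prior opioid status, including the site-by-time terms if those should differ by group.
- Report the interaction estimate with its 95% confidence interval, beside the two subgroup effects and their intervals from the same model.
- Say that any statement of a differential effect will rest on that interaction, not on two separate p-values.
- Define the grouping variable once: the protocol speaks of an active prescription at the index visit, the SAP of prior prescriptions.

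The cost is a few terms and a short paragraph. Prior opioid status is already in the opioid models. The small downside is that covariate and random effects not interacted with prior opioid status are assumed common to both groups, which separate fits would not require.

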Hypothesis 1b: Time periods during which clinics are randomly assigned to receive the modified imaging reports will have a lower rate of subsequent opioid prescriptions than time periods during which clinics do not receive modified reports.

Aim 1c: To determine if inserting epidemiological evidence decreases subsequent cross-sectional imaging magnetic resonance (MR) and computed tomography (CT).

Hypothesis 1c: Time periods during which randomly assigned clinics receive modified imaging reports will have a lower rate of subsequent cross-sectional imaging than time periods for which clinics do not.

Aim 1d: To explore whether adding epidemiological evidence decreases overall costs of care for low back pain based on CMS reimbursement.

Hypothesis 1d: Clinics that are randomly assigned to receive the modified imaging reports will have lower back pain-related estimated payer costs than clinics whose patients do not receive modified reports. Costs are another outcome that are highly relevant to both patients and health systems.

Aim 2: To determine whether inserting age-specific prevalence of imaging findings in asymptomatic subjects has a differential effect on subsequent back-related interventions if inserted into lumbar spine MR and CT imaging reports compared with plain films.

Hypothesis 2: Inserting epidemiological information into plain film reports will result in a greater decrease in subsequent back-related interventions than similar information put into MR and CT reports. Given that plain films are generally obtained earlier in the course of back pain and more frequently than MR and CT, the potential impact of inserting epidemiological information into plain film reports is large.

Aim 3: To determine if specific imaging findings influence subsequent interventions.

Hypothesis 3: Inserting the statement will result in a greater decrease in subsequent interventions for patients without clinically important findings compared with patients who have clinically important imaging findings. Our work and others have shown that certain imaging findings are likely to be clinically more important than others (e.g. nerve root compression, moderate to severe central stenosis, disc extrusions). We expect that patients without these more important findings will have a greater reduction in subsequent interventions.

4. Study Details

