**Analysis for Aim 2:** The hypothesis of Aim 2 is that there will be a differential effect of the intervention according to the imaging modality used. In order to test this hypothesis we will analyze patient-level data according to the appropriate LMM or GLMM given above, but including the interactions between  $Modality_{ijk}$  indicators (modeled using two indicator variables coding CT and MR, with plain film as the reference) and  $Status_{kt}$ . A test of the interaction terms (2 degree of freedom Wald test) will be used to test the null hypothesis that the effect of the intervention does not vary according the imaging modality.

**Analysis for Aim 3:** The hypothesis of Aim 3 is that there will be a differential effect of the intervention according to the results that are found in the imaging report. We will use an additional variable,  $ImageFinding_{ijk}$ , that takes the value 1 if a significant image finding is present, and 0 otherwise (see detail regarding variable specification in protocol). We will test the null hypothesis that the interaction between  $ImageFinding_{ijk}$  and  $Status_{kt}$  is zero using a Wald test.

[figure not shown]
**Power Calculations:** Our UH2 efforts with respect to sample size and statistical power focused on two key items. First, an important aim of our UH2 Working Group 2 was to obtain an accurate clinic and provider count for each health system. We will now randomize  $n=110$  clinics (1,824 PCPs), which is slightly lower than the  $n=128$  clinics (1,898 PCPs) assumed in our initial project application. However, the majority of the clinics that were dropped were those with only one PCP and therefore would not have contributed much information to the analysis. Second, in our Working Group 3 we sought to develop and characterize a composite RVU summary to be used as the primary outcome measure in this study. In our UH2 project application we discussed statistical power in the context of an important secondary outcome measure, a reduction in subsequent opioid prescription rates. We now present statistical power for the primary outcome measure using data from the BOLD Registry to inform key design parameter estimates.

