
 
• Clinical importance of imaging findings
 
	To assess the impact of image findings on the treatment effect, the SAP and protocol paper specified that a binary measure indicating the presence of a clinically important finding would be used. We instead decided to use a three-category measure so that we could measure effect modification among the following groups: patients with likely clinically important findings, patients without likely clinically important findings but with one of the findings included in the LIRE intervention text, and patients without either of these types of finding.

Lumbar Imaging Reporting with Epidemiology (LIRE)  
STATISTICAL ANALYSIS PLAN

Outcomes	

• Opioid prescriptions

	The original SAP defined the opioid outcome as a binary indicator of opioid prescriptions within 90 days, which is the same outcome that we use in the manuscript. When we were writing the protocol paper we thought that morphine equivalent dose (MED) would be more sensitive to the intervention since it could capture reductions in the amount of opioids within prescriptions. However, we discovered that some sites had high missingness for prescription characteristics that we needed to calculate MED. We also encountered challenges identifying duplicate prescriptions. We concluded that it would be better to revert to our original opioid measure for which we would have considerably greater accuracy.

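### The Aim 3 rule for clinically important findings lists central canal stenosis with no severity grade, although the protocol's own rationale uses moderate to severe stenosis; coding mild stenosis as important can dilute the interaction

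*Protocol*

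**What the plan says.** **Rationale, with a grade.** Under Hypothesis 3, Protocol section 3 gives as examples of more important findings "nerve root compression, moderate to severe central stenosis, disc extrusions". Protocol 5.7, Aim 3, repeats the examples: "certain imaging findings are likely clinically more important than others (e.g. nerve root compression, moderate to severe central stenosis, disc extrusions".

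**Classifying rule, without a grade.** The same paragraph of Protocol 5.7 says the radiology result will be used "to categorize imaging findings into clinically important versus not clinically important" and then gives the list: "We have identified central canal stenosis, nerve root compression and disc extrusion (a type of herniation) as the clinically most important imaging findings". It continues: "This is in contrast to findings that are less clinically important (disc bulge, disc narrowing, Modic change, annular fissure, etc".

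**SAP, Analysis for Aim 3.** The indicator "takes the value 1 if a significant image finding is present, and 0 otherwise (see detail regarding variable specification in protocol". The SAP body contains no list of its own.

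**SAP Revisions.** The binary measure is replaced by one with three levels. The top level is for those whose images show something likely to matter clinically. The middle level is described as "patients without likely clinically important findings but with one of the findings included in the LIRE intervention text". The last level covers those who have neither kind. The amendment does not list the important findings or mention a stenosis grade.

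**Related places.** Protocol Table 3 has a row for stenosis limited to moderate or severe. Protocol 4.1 and 4.3 set broad eligibility, with no exclusion for fracture, tumour or infection.

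**The concern.** The only list of important findings in the two documents is the ungraded one. A person or program coding reports from it would set the indicator for any central canal stenosis, including mild. Someone coding from the rationale would not. Both could cite the same paragraph of Protocol 5.7.

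Hypothesis 3 expects a larger reduction in interventions among patients without important findings, and Protocol 5.7 places the primary inference for Aim 3 on the interaction. If mild stenosis behaves like an incidental finding, putting it in the important group pulls the two group effects together. Aim 3 could then look null even though the effect differs as hypothesised, and the cause would be the definition rather than the abstraction.

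A second, smaller question is where a vertebral fracture, neoplasm or infection belongs. None is on either list, and eligibility does not remove such patients.

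**Working it through.** The documents state no power, effect size or misclassification rate for Aim 3, so there is no planned figure to reproduce.

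**1. Is grade meaningful in the protocol's own data?** Table 3, moderate or severe stenosis by age group: (2 + 3 + 4 + 6) / (31 + 53 + 35 + 29) = 15/148 = 10.1%. Mild stenosis is not reported. This is an MR sample of people without back pain, so it does not give a rate for the trial population.

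**2. Dilution from mild stenosis.** For a misclassified two-level modifier,

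observed interaction = true interaction × (PPV + NPV − 1),

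provided misplaced patients respond like their true class and the errors do not depend on intervention status. Let p be the share with truly important findings and m the share of the remaining patients with mild stenosis alone. With NPV = 1 the factor is PPV = p / (p + (1 − p)m). Both inputs are assumptions.

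| p | m | Calculation | Factor |
|---|---|---|---|
| 10% | 10% | 0.10/0.19 | 0.53 |
| 10% | 20% | 0.10/0.28 | 0.36 |
| 20% | 10% | 0.20/0.28 | 0.71 |
| 20% | 20% | 0.20/0.36 | 0.56 |
| 30% | 10% | 0.30/0.37 | 0.81 |
| 30% | 20% | 0.30/0.44 | 0.68 |

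**3. Unlisted serious findings alone.** Let f be the share of all patients with such a finding coded as not important. With p = 10% and no mild stenosis, NPV = (1 − p − f)/(1 − p). For f = 1% this is 0.89/0.90 = 0.99; for f = 5% it is 0.85/0.90 = 0.94.

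**4. Both together.** Take 10% important, 5% of all patients with mild stenosis only, and 3% unlisted serious. PPV = 0.10/0.15 = 0.667 and NPV = 0.82/0.85 = 0.965, so the factor is 0.63. Most of the loss comes from the missing grade.

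**5. Dependence on how misplaced patients respond.** Keep the 10% and 5% and ignore unlisted findings. If mild-stenosis patients respond exactly like the important group, the factor is 1.00. If they show half the effect seen in patients without important findings, it is 1 − (0.05 × 0.5)/0.15 = 0.83. If they show all of it, it is 0.67.

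**The case against.** The strongest reply is that the grade never appears in a hypothesis sentence. It stands in the explanatory text, inside a list of examples, and the ungraded list in the same paragraph names the same three findings. It can therefore be read as shorthand, and nowhere do the documents say that mild stenosis is coded as important. That is fair, but a coding rule has to work without the reader supplying the grade, and neither the SAP body nor its revisions settles it.

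It can also be said that the three-category amendment supersedes the binary rule, so the list now in force is not known. This stands as a limit on certainty. It also means the amendment gives no definition to replace the one in Protocol 5.7.

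Two stronger readings are tempting and are not supported:

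- **That the interaction is attenuated as a matter of fact.** The documents give neither a prevalence of mild stenosis in imaged patients nor any subgroup effect. The factor is 1.00 if the misplaced patients respond like the group they are placed in. The formula is for two groups, whereas the current plan has three. One pair of rates is also applied across modalities, although the protocol says plain films are the more frequent test.
- **That fracture, tumour and infection are assigned to the unimportant group.** The documents do not say so. The protocol names the most important findings, and its contrasting list is open-ended. Under the amendment, if the list is unchanged, such patients would fall in the text-finding group or the neither group, depending on their other findings. No figure shows how often each would occur.

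**Conclusion.** The mismatch within the protocol is real and unresolved: the rationale and Table 3 use moderate or severe stenosis, the classifying sentence does not, and the SAP relies on that sentence. Followed as written, the rule places mild stenosis in the important group, against the protocol's own reasoning.

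The consequence is conditional. The range of 0.36 to 0.81 rests on assumed prevalences, a two-group approximation, and mild-stenosis patients responding like incidental-finding patients. It shows that the loss could be large, not that it is.

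The point about fracture, neoplasm and infection holds by inference only, and its expected effect is small (0.94-0.99 on its own under the rates above).

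The primary test of the overall intervention effect does not use this variable and is unaffected.

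**What to change.** 1. In Protocol 5.7, Aim 3, and in the SAP Revisions entry, define the likely clinically important category as moderate or severe central canal stenosis, nerve root compression, or disc extrusion. Put the list in the SAP itself, so that it no longer depends on a cross-reference.
2. State a default category for reports that mention stenosis without a grade.
3. Run the ungraded coding, in which any central canal stenosis counts as important, as a sensitivity analysis for the Aim 3 interaction.
4. In the same abstraction, flag fracture, neoplasm and infection and keep those patients out of the comparison groups for the Hypothesis 3 contrast, for example as a separate level.

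**Cost.** A revised coding list for the report abstraction already planned in Protocol Table 6 and a short SAP text. Some ungraded reports will be assigned by default, which brings some misclassification of its own; the sensitivity analysis shows how much the result depends on the stenosis coding. The SAP Revisions describe models already used for a manuscript. If abstraction is complete, the change means re-coding reports, and the result should be labelled as a later analysis.
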